## **Subgroup Analyses**

To examine the heterogeneity of the treatment effect, subgroup analyses for the primary and secondary endpoints will be performed in order to explore whether the treatment effect is consistent across subgroups. Subgroup analyses to evaluate variation in the effect of treatments will be performed using interaction terms within the Cox proportional hazards model. For binary variables, we will include the subgroup factor as a stratification variable within the Cox regression model. This model structure will decrease the reliance on the proportional hazards assumption. Additionally, treatment effects within each categorical subgroup will be examined separately using Cox proportional hazards models. Event rates by treatment and HRs with 95% confidence intervals will be reported for each subgroup. Forest plots will be generated displaying the estimated hazard ratios and 95% confidence intervals for each subgroup. For subgroups defined using continuous variables, the analysis based on the continuous form will be considered primary but for display purposes these variables can also be categorized.

We have pre-specified sex, minorities, age greater than 70, myocardial infarction location (anterior MI or not), type of diabetes (1 or 2), insulin treatment of diabetes, use of statin therapy at baseline (for the OMVM analyses only), known peripheral artery disease at baseline as key subgroups of interest. There are also pre-specified analyses by tertiles of lead and cadmium as indicated above. The examination of these pre-specified subgroups will include formal tests of interaction within the Cox regression model.

## **10. DATA COLLECTION AND QUALITY ASSURANCE**

### **10.1 Data Collection Forms**

A validated Electronic Data Capture (EDC) system will be used for this study. The majority of the study data will be transcribed by study personnel from the source documents onto an eCRF and transmitted in a secure manner to the DCC. All data relating to the study must be recorded in eCRFs developed by DCRI and approved by the study sponsor. Data must be entered into eCRFs in English. The investigator's electronic signature, a compliant platform (21 CFR Part 11) is recorded in the database as verification that all data are complete and accurate.

### **10.2 Data Management**

Data will be processed using a validated computer system conforming to regulatory requirements.

Computerized data will be accessible only by password, and a centralized monitoring system will record and report all access to data. The DCRI computer network is protected by a firewall. Electronic CRFs (eCRFs) will be identified by study number only, to ensure participant anonymity. No participant identifiers will be used in the presentation of data. Except when required by law, participants will not be identified by name, personal identification number (e.g., social security number in US and Canada,

address, telephone number) or any other direct personal identifier in study records. This information will be retained by each individual center and will not be disclosed to the Clinical or Data Coordinating Center except as needed for centralized clinical, quality of life and economic follow-up of the participants. Participants will be informed that the study physician and his/her study team will report the results of study-related tests to the Clinical and Data Coordinating Center and to the NIH. Participants will be informed that their records may be reviewed in order to meet federal, state or regional/local regulations. Reviewers may include the CCC/DCC monitors, IRBs/ECs, the NIH, other government regulators as dictated by local law, or their delegates.

Records of patients, source documents, monitoring visit logs, eCRFs, inventory of study product, regulatory documents, and other sponsor correspondence pertaining to the study must be kept in the appropriate study files at the site. Source documents include all recordings and observations or notations of clinical activities and all reports and records necessary for the evaluation and reconstruction of the clinical study. These records will be retained in a secure file for the period required by the institution or site policy. Prior to transfer or destruction of these records, the DCC must be notified in writing and be given the opportunity to further store such records.

### **10.3 Quality Assurance**

Greater detail will be found in the MOP for the TACT2 and the individual Manuals for the Metals Lab and Biorepository. Steps to be taken to ensure the accuracy and reliability of data include:

- the selection of qualified investigators and appropriate study centers.
- review of protocol procedures with the investigator and associated personnel before the study.
- periodic monitoring visits to clinical sites, central pharmacy, metals lab, and biorepository.
- written instructions will be provided for collection, preparation, and shipment of blood and plasma samples.
- electronic CRF completion guidelines will be provided and reviewed with study personnel before the start of the study.
- The DCRI CRA will review eCRFs for accuracy and completeness during site monitoring; any discrepancies will be resolved with the investigator or designee, as appropriate.

At regular intervals, all data will be transferred from the EDC database to SAS for statistical summarization, data description, and data analysis. Further cross-checking of

the data will be performed in SAS, and discrepant observations flagged and appropriately resolved through a data query system.

#### **10.3.1 Training**

Training procedures will be described in the MOP. Site training, in particular, will be provided via in-person study meetings as well as online training.

#### **10.3.2 Quality Control**

The Data Coordinating Center will perform internal database quality-control checks, and data audits throughout the course of the trial, as well as coordinate blinded repeat metals analyses in a statistically valid proportion of samples.

#### **10.3.3 Metrics**

The Clinical Events Committee at the Brigham and Women's Hospital will adjudicate all components of the primary endpoint except for coronary revascularization. Coronary revascularization will be clinically confirmed by the Clinical Events Committee.

#### **10.3.4 Protocol Deviations**

Documentation and management of protocol deviations will be the responsibility of the DCRI Site Management team. Incidences identified will be discussed with the site investigator and study team for corrective action and follow-up with their IRB.

#### **10.3.5 Monitoring**

The DCRI Site Management team will be responsible for:

- verifying that the appropriate assurances and certification of training in the protection of human subjects are in place prior to the initiation of any protocol.
- providing education to all site staff regarding the conduct of clinical studies according to good clinical practices.
- assisting sites in the development of informed consent templates to make sure that they contain appropriate elements.
- ensuring that the CRA monitors each site according to the approved comprehensive monitoring plan.
- assuring during the site initiation visit that the site has adequate facilities/staff integral to the successful operation of the study. The site initiation visit may also be utilized to conduct training regarding regulatory compliance or individual protocol procedures.

- tracking recruitment of patients entered updating relevant trial information on the trial web site.

#### **10.4 Medical Information Coding**

For medical information, the following thesauri will be used:

- Latest version of MedDRA for adverse events, and
- World Health Organization Drug Dictionary for concomitant medications.

### **11. PARTICIPANT RIGHTS AND CONFIDENTIALITY**

#### **11.1 Institutional Review Board (IRB) Review**

All TACT2 sites will submit the study protocol, informed consent form, and other study documents to their corresponding IRB for approval. Any amendments to the protocol, other than minor administrative changes, must be approved by each IRB before they are implemented.

#### **11.2 Informed Consent Forms**

TACT2 sites will obtain informed consent from each study participant prior to randomization. Trained personnel as listed in the Delegation of Authority log will obtain consent. In all cases in which the patient does not have an understanding of English, sites will obtain an IRB approved translation of the study consent to present to the patient. Patients will have ample opportunity to review the consent form, ask questions, and make an informed decision on risks and benefits.

#### **11.3 Participant Confidentiality**

Overall policy: Any data, specimens, forms, reports, video recordings, and other records that leave the site will be identified only by a participant identification number (Participant ID, PID) to maintain confidentiality. All records will be kept in a locked file cabinet. All computer entry and networking programs will be done using PIDs only. Information will not be released without written permission of the participant, except as necessary for monitoring by IRB, the FDA, the NCCIH, and the OHRP.

Exceptions to the policy:

1. The Study Pharmacy, following standard regulatory procedures, will deliver a - specific prescription for each study infusion. As such, they will know PHI for each patient. The PHI for each patient will be kept in a secured pharmacy computer, behind a firewall, and will be known to a minimum number of pharmacy personnel.
2. The DCRI Call Center will make the initial patient follow-up by phone. As such, they will need to know PHI including patient name, next-of-kin, etc. Again, this information will be kept secured in the DCRI Call Center.

## **11.4 Study Discontinuation**

Procedures for study discontinuation will be detailed in the TACT2 MOP.

## **12. COMMITTEES**

### **The Steering Committee**

The main governing body and decision-making committee for the trial and assumes overall responsibility for the design, quality control, and conduct of the study. All major scientific decisions will be discussed with the Steering Committee. The Steering Committee will review the baseline characteristics and pooled event rate after 70 primary endpoint events have occurred. The Steering Committee will determine whether the patient population or sample size needs to be modified.

### **Executive Committee**

The Executive Committee is advisory to the Steering Committee and is responsible for objective evaluation for the course of the trial, design and conduct. Recommendations for all scientific decisions will be made to the Steering Committee.

### **Biorepository Committee**

This committee will coordinate communication between Columbia University, the CDC and DCRI on aspects related to sample collection, shipments and laboratory analysis (for metals); keep track of shipments (both specimen collection kits and samples) and samples collected, received, processed, stored and analyzed (for metals); troubleshoot any problems as they arise and report to the TACT2 operations committee.

### **Operations Committee**

This subcommittee of the Steering Committee will provide oversight for the day-to-day progress of the study.

### **Publications, Presentations and Ancillary Studies (PPAS) Committee**

The objectives of this committee will be to facilitate timely dissemination of study findings, maintain high scientific standards for published material, prioritize the order of publication and presentations, and ensure equitable investigator participation and attribution of authorship. The committee will ensure publications are well-aligned with the trial's research agenda and are not redundant. The PPAS committee will review all proposals for data analysis, as well as research abstracts, presentations, and manuscripts before submission. The committee will also review proposals for ancillary studies. The committee will also ensure that each publication that meets NIH Open Access criteria is deposited in PubMed Central.

### **Committee for the Recruitment of Women and Minority Subjects**

Recruitment of women and minority subjects is a critically important part of developing a clinical trial whose results can be generalized to the overall US population. The TACT2 leadership has therefore constituted a committee of experts to assist in enhancing recruitment of women and minority subjects. They will report to the Steering Committee

with suggestions as to how to increase the enrollment of women and minorities. Some of these activities are covered earlier in this document.

### **Data-Driven Trial Management Committee**

The objectives of this committee will be to:

- review the established mapped key risk indicators and triggers (thresholds)
- modify the risk levels where indicated
- document actions taken and results
- provide summary report of findings by subject, site, and study levels to study leadership.

## **13. PUBLICATION OF RESEARCH FINDINGS**

Publication of the results of this trial will be governed by the policies and procedures developed by the Steering Committee, and the PPAS Committee. Both Committees will have NIH scientists as members. Any abstract, manuscript or major presentation will be made available for review by NIH, in accordance with NIH policies, prior to submission. Per NIH policies, a public data set that is not identifiable will become available when the study has been completed.

Abbreviations

Abbreviation	Definition
CEC	Clinical Events Committee
CI	Confidence Interval
CONSORT	Consolidated Standards of Reporting Trials
CRF	Case Report Form
CSR	Clinical Study Report
DCRI	Duke Clinical Research Institute
EDC	Electronic Data Capture
FU	Follow-Up
HR	Hazard Ratio
ITT	Intention-To-Treat
MI	Myocardial Infarction
MITT	Modified Intention-To-Treat
NDI	National Death Index
OMVM	Oral MultiVitamins and Multiminerals
SAE	Serious Adverse Event
SAP	Statistical Analysis Plan
TACT2	Trial to Assess Chelation Therapy 2
WLW	Wei, Lin, and Weissfeld

1 Introduction

The purpose of this Statistical Analysis Plan (SAP) is to describe the analyses and data presentations that will be used for the creation of the primary manuscript of the study which will focus on the comparison of active chelation vs. placebo chelation.

1.1 Study Design

The Trial to Assess Chelation Therapy 2 (TACT2) is a randomized, double blinded, placebo-controlled 2x2 factorial clinical trial. The study treatments are edetate disodium-based chelation (weekly infusion for 40 weeks) and high-dose oral multivitamins and multi-minerals (OMVM) (twice daily for up to 5 years). Subjects with diabetes mellitus with a prior myocardial infarction (MI) are recruited from participating sites in the US and Canada and randomized in a 1:1:1:1 fashion to 4 groups:

- i. Active chelation + active OMVM
- ii. Active chelation + placebo OMVM
- iii. Placebo chelation + active OMVM
- iv. Placebo chelation + placebo OMVM.

Patients will be followed for clinical events until the earlier of database lock or five years from randomization. Clinical outcomes will be collected by study sites at each infusion visit and by the DCRI Call Center at month 6 and 12, and every 4 months afterwards with the last assessment at month 60.

TACT2 is an event driven trial with a plan to continue until at least 282 primary endpoint events are identified. The original planned sample size was 1200 participants. The sample size was later modified to 1100. The final enrollment is 1000, but with an increased follow-up time to preserve statistical power. More details on sample size and power calculation are included later in the SAP.

1.2 Study Objectives

TACT2 seeks to replicate TACT, which found a reduction of recurrent cardiovascular events most prominent in the subgroup of post-MI diabetic patients receiving edetate disodium-based chelation therapy.

1.2.1 Primary Objective

The primary objective of TACT2 is to determine if the chelation-based strategy increases the time to the first occurrence of any of the components of the primary composite endpoint of all-cause mortality, MI, stroke, coronary revascularization, or hospitalization for unstable angina compared with the placebo chelation strategy.

1.2.2 Secondary Objectives

The secondary objectives of TACT2 are to determine:

- i. if the chelation-based strategy reduces the overall rate of occurrence of the events which define the primary composite endpoint of all-cause mortality, MI, stroke, coronary revascularization, or hospitalization for unstable angina events compared with the placebo chelation strategy.
- ii. to determine if the chelation-based strategy increases the time to the first occurrence of a secondary composite endpoint of cardiovascular mortality, MI, or stroke compared with the placebo chelation strategy.
- iii. to determine if the chelation-based strategy increases the time to all-cause mortality compared with the placebo chelation strategy.

1.2 Sample size Considerations

The study was originally designed to enroll 1200 participants with a minimum follow-up of 12 months. Since the enrollment was slower than projected, the DSMB conducted a blinded review of enrollment aggregate event rates, and projected event rates in July 2019. The study team proposed a new sample size based on the updated projected event rate, an assumed hazard ratio of 0.7 comparing chelation and placebo, and a dropout rate of 5% (Table 1). While the sample size was reduced to 1100 with an extended enrollment time by December 2020, the follow-up (FU) period was extended to 2 years to ensure to have the targeted power of 85%.

The final study enrollment was 1000. The study team evaluated the study power with a newly extended FU period of 2.5 years assuming various dropout rates (Table 2). Even with a dropout rate of 10%, the study power exceeds the targeted power of 85% with 1000 participants and 2.5 years of follow-up.

The full details around sample size adjustment and study power are included in Appendix I.

Table 1. Original and modified sample size and study power

Sample size	Note	Power	Overall event rate (%/pt-yr)	Assumed event rate in EDTA (%/pt-yr)	Assumed event rate in Placebo (%/pt-yr)	Dropout rate	Enrollment year	FU year	Total # events
1200	Original sample size	85%	10.9%	8.97%	12.81%	2%	3	1	282
1100	Modified sample size	88%	9.2%	7.56%	10.82%	5%	4.25	2	308

Table 2. Study power with the final 1000 participants enrolled

Scenario	Overall event rate (%/pt-yr)	Assumed event rate in EDTA (%/pt-yr)	Assumed event rate in Placebo (%/pt-yr)	Overall dropout rate	Mean power	Mean # events
Projected	8.8	7.2	10.4	5%	89%	299
				7%	88%	295
				10%	87%	288

2 General Considerations for Data Analyses

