### **9.2 Sample Size and Randomization**

Participants will be randomized in a 1:1:1:1 allocation ratio using simple randomization. The study was originally designed to enroll a total of 1200 participants with a minimum follow-up of 12 months. The DSMB conducted a blinded review of enrollment aggregate event rates, and projected event rates in July 2019. Following this blinded review, the

DSMB recommended a reduction in the target sample size to 1100 participants and an increase in the minimum follow-up from 1 year to approximately 2.5 years. Due to slowed enrollment related to the COVID-19 pandemic, in the fall of 2020, the DSMB and the NIH leadership agreed to a proposal to complete enrollment by 12/31/2020 with an allowance to follow the study participants until there are enough primary endpoint events to maintain 85+% power.

Several design factors and research objectives have been considered in developing an appropriate sample size for the TACT2 study. First, patient enrollment and follow-up has been determined so there would be a sufficient number of endpoints to provide a high degree of confidence for testing the primary hypothesis. Second, the statistical power for secondary endpoints has been considered. Finally, the sample size has been determined to provide a reasonable level of confidence for detecting clinically important differences in outcome between treatment strategies even if current projections of event rates and hypothesized differences in clinical outcomes between the treatment groups prove to be optimistic.

Table 3 shows the required number of endpoint events to have 80% to 90% power with hazard ratios varying from 0.50 to 0.75. The two factors (EDTA chelation and OMVM) are assumed to be additive for the sample size calculations. Based on TACT we anticipate a hazard ratio of 0.70 (active chelation vs. placebo chelation) to determine the sample size requirements. This hazard ratio assumption is very conservative compared to the observed effect in TACT. Assuming a two-sided 0.05 type I error rate and approximately 5% consent withdrawal or loss-to-follow-up per year, the final sample size of 1000 participants will provide approximately 85% power to detect a hazard ratio of 0.70 for the primary endpoint of time to all-cause mortality, myocardial infarction, stroke, coronary revascularization, or hospitalization for unstable angina comparing active chelation vs. placebo chelation.

Table 3. Required number of events						

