	HR=0.50	HR=0.55	HR=0.60	HR=0.65	HR=0.70	HR=0.75
80% power	65	88	120	169	247	379
85% power	75	100	138	194	282	434
90% power	87	118	161	226	330	508

Calculations performed using nQuery 7.0 and assume a 0.05 type I error rate (two-sided) with 1:1 randomization.

For other exploratory endpoints, we outline a general power justification for comparisons to be made among the four arms of the 2x2 factorial design. We anticipate that roughly 1000 participants will have blood and urine samples available from baseline and one or more follow-up time points. A sample size of 250 participants per group will provide 80% or greater power for any between group differences greater than  $\frac{1}{4}$  of a standard deviation. These calculations are based on a two-sample t-test and assume a two-sided type I error rate of 0.05.

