Appendix I. TACT2 Sample size and study power projections as of March 1, 2021

1. Enrollment and timeline

- a. 1000 patients enrolled.

Last rand subject infusion	Last rand subject Follow-up	Last endpoint adjudicated	Database lock
December 2021	June 2023	August 2023	October 2023

2. Event rate in the TACT diabetic cohort (n=633)

- a. EDTA: $7.8\%/\text{pt-yr} = 80 \text{ events} / 1031 \text{ patient-years}$
- b. Placebo: $13.2\%/\text{pt-yr} = 117 \text{ events} / 886 \text{ patient-years}$
- c. Hazard ratio: 0.59

3. Original and modified sample size and power

Sample size	Enrollment	FU	Power	Hazard ratio (EDTA/placebo)	Overall event rate (%/pt-yr)	Assumed event rate in EDTA (%/pt-yr)	Assumed event rate in Placebo (%/pt-yr)	Total # events
1200	3 years	1 year	85%	0.7	10.9	8.97	12.81	282
1100	3 years + 15 months	2 years	88%	0.7	9.2	7.56	10.82	308

4. Statistical power with 1000 enrolled participants as of March 1, 2021

- a. As of February 23, 2021, 137 patients with at least one adjudicated primary endpoint, 1990 patient-years from 1000 enrolled patients
 - i. Proportion of reported events adjudicated as primary endpoints = 69%
 - ii. Projected overall event rate: If 39 patients had an adjudicated primary endpoint out of 57 additional patients with at least one reported event, $176/1990 = 8.8\%/\text{pt-yr}$
 - iii. Minimum overall event rate: $137/1990 = 6.9\%/\text{pt-yr}$
 - iv. Optimistic overall event rate: If 45 patients had an adjudicated primary endpoint out of 57 additional patients with at least one reported event, $182/1990 = 9.1\%/\text{pt-yr}$
- b. Assumptions for simulations with 10K iterations per scenario
 - i. No re-consent for those who run out 5 years from the initial consent
 - ii. Constant parameters: a two-sided alpha=0.05, hazard ratio of EDTA to placebo=0.7, sample size=1000, FU=2.5 years
 - iii. Overall dropout rate: 5, 7, 10%
 - iv. Overall event rate: 6.9, 8.8, 9.1%/pt-yr

Scenario	Overall event rate (%/pt-yr)	Assumed event rate in EDTA (%/pt-yr)	Assumed event rate in Placebo (%/pt-yr)	Overall dropout rate	Mean power	Mean # events
Projected	8.8	7.2	10.4	5%	89%	299
				7%	88%	295
				10%	87%	288
Minimum	6.9	5.7	8.1	5%	78%	244
				7%	77%	240
				10%	76%	235
Optimistic	9.1	7.5	10.7	5%	88%	307
				7%	87%	303
				10%	86%	297

[**Appendix II. Details of two participants who were randomized from two different sites**](#)

Double randomization case 1

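### SAP Table 2 and Appendix I item 4 state powers that match rounded arm rates, not the constant hazard ratio of 0.7; the errors are at most about 2 points and no conclusion changes

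*SAP*

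**What the plan says.** SAP section 1.2 (Sample size Considerations) presents Table 2 as the power assessment for the final enrollment: "The study team evaluated the study power with a newly extended FU period of 2.5 years assuming various dropout rates (Table 2". It concludes: "Even with a dropout rate of 10%, the study power exceeds the targeted power of 85% with 1000 participants and 2.5 years of follow-up".

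Appendix I item 4 gives the settings. The powers come from simulation ("Assumptions for simulations with 10K iterations per scenario") with "Constant parameters: a two-sided alpha=0.05, hazard ratio of EDTA to placebo=0.7, sample size=1000, FU=2.5 years". Each scenario lists an overall event rate, two arm rates to one decimal, three dropout levels, a mean power and a mean event count. Table 2 repeats only the Projected scenario.

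Dropout is listed as "Overall dropout rate: 5, 7, 10" (per cent), with no time unit or start date. The Table 1 text is similar: "an assumed hazard ratio of 0.7 comparing chelation and placebo, and a dropout rate of 5% (Table 1". Protocol section 9.2 assumes about 5% per year.

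Protocol section 9.2 also provides a check: "Table 3 shows the required number of endpoint events to have 80% to 90% power with hazard ratios varying from 0.50 to 0.75". Its footnote reads: "Calculations performed using nQuery 7.0 and assume a 0.05 type I error rate (two-sided) with 1:1 randomization".

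**The concern.** With one hazard ratio, one alpha and 1:1 allocation, power depends almost entirely on the number of events, so more events must mean more power. Appendix I breaks this order between the Projected and Optimistic scenarios at all three dropout levels. The Projected powers look too high for their event counts, and the Minimum powers too low.

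Table 2 is the SAP's justification for 1000 patients, and its closing sentence turns on the margin over 85% at 10% dropout. A reader should be able to recover that margin from the stated hazard ratio and event count, and should know which dropout assumption it rests on.

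**Working it through.** **Inputs.** Two-sided alpha 0.05, HR 0.7, arm rates, event counts and powers: SAP Table 2 and Appendix I item 4. Required events at HR 0.70: protocol Table 3. Allocation for chelation against placebo chelation: 1:1.

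**Formula (Schoenfeld).** Power = Φ(½ × √d × |ln HR| − 1.96), where d is the number of events and |ln 0.70| = 0.3567. Required events: d = 4 × (1.96 + z)² / (ln HR)², where z is the normal quantile for the target power.

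**Step 1: reproduce the plan's own figures.** At HR 0.70 the formula requires 246.8, 282.3 and 330.4 events for 80, 85 and 90% power; protocol Table 3 prints 247, 282 and 330. For SAP Table 1 it gives 85.0% at 282 events (stated 85%) and 87.9% at 308 (stated 88%). The two-decimal rates in Table 1 have ratios 8.97/12.81 = 0.700 and 7.56/10.82 = 0.699.

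**Step 2: apply it to the nine rows.** Example, Projected at 5% dropout: ½ × √299 × 0.3567 = 3.084; 3.084 − 1.96 = 1.124; power 86.9%. With the printed rates, 7.2/10.4 = 0.692: 3.179 − 1.96 = 1.219; power 88.9%. The stated value is 89%, which at HR 0.70 would need about 319 events.

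| Scenario (rate ratio) | Dropout | Events | Stated | At HR 0.70 | At printed ratio |
|---|---|---|---|---|---|
| Projected (0.692) | 5% | 299 | 89 | 86.9 | 88.9 |
| | 7% | 295 | 88 | 86.5 | 88.4 |
| | 10% | 288 | 87 | 85.7 | 87.7 |
| Minimum (0.704) | 5% | 244 | 78 | 79.6 | 78.4 |
| | 7% | 240 | 77 | 78.9 | 77.7 |
| | 10% | 235 | 76 | 78.1 | 76.8 |
| Optimistic (0.701) | 5% | 307 | 88 | 87.8 | 87.6 |
| | 7% | 303 | 87 | 87.4 | 87.1 |
| | 10% | 297 | 86 | 86.7 | 86.5 |

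At HR 0.70 the Projected powers are overstated by 1.3 to 2.1 points and the Minimum powers understated by 1.6 to 2.1. At the printed ratios all nine rows agree within 1 point.

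**Step 3: the ordering.** From Projected to Optimistic, events rise (299 to 307, 295 to 303, 288 to 297). At HR 0.70 power should rise by 0.9, 0.9 and 1.0 point. The stated power falls by 1 point each time. The Monte Carlo standard error of a difference between two powers from 10,000 iterations is about 0.5 point.

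**Step 4: implied hazard ratio.** Allowing for rounding to a whole per cent, the stated powers imply an HR of 0.690–0.697 for Projected and 0.703–0.708 for Minimum. The ranges do not overlap.

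**Step 5: unrounded rates.** For overall rate r and HR 0.70, placebo = 2r/1.7 and EDTA = 0.7 × placebo. This gives 7.25/10.35 for r = 8.8, 5.68/8.12 for 6.9 and 7.49/10.71 for 9.1 (%/pt-yr). Rounding each to one decimal gives the printed pairs.

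**Step 6: check by simulation.** Log-rank test, 10,000 iterations per cell. Assumptions: uniform accrual over 4.0 years, 2.5 years minimum follow-up, 5-year cap, dropout read as cumulative.
- Projected, 5%: 300 events; 86.9% with unrounded rates, 89.0% with 7.2/10.4 (stated 299, 89%).
- Minimum, 5%: 244 events; 79.7% unrounded, 77.9% with 5.7/8.1 (stated 244, 78%).
- Projected, 10%: 292–293 events; 85.6% unrounded, 88.3% rounded (stated 288, 87%), a looser match.

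**Step 7: dropout unit.** Under the same assumptions, cumulative dropout of 5/7/10% gives 300/297/292 Projected events against the stated 299/295/288. Annual dropout starting at the February 2021 data cut gives 299/297/293, so the counts cannot separate these two readings. The protocol's 5% per year from randomization gives 277, 279 and 282 events with uniform accrual over 4.0, 4.25 and 4.6 years. By the formula that is 84.3 to 85.0% power at HR 0.70; direct simulation at 4.0–4.25 years gave 83.5–84.3%.

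**The case against.** The strongest reply is that the powers agree with the arm rates printed in the same rows, and that 0.692, 0.704 and 0.701 all round to the stated 0.7. On that view nothing is wrong and the odd ordering follows from disclosed inputs. The agreement is real, and it is why this is minor. It does not remove the point: Appendix I calls the hazard ratio constant, the two-decimal rates in Table 1 give 0.699–0.700, and protocol section 9.2 uses 0.70, so 0.70 was intended.

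Other replies also carry weight. Seven of the nine rows are within 2 points at HR 0.70, and the other two miss by barely more. The three inverted pairs may not be independent, because the SAP does not describe its random seeds, so their evidence should not simply be added up. Appendix I is dated March 1, 2021, and the trial is event driven, so delivered power depends on the events reached.

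A reader might infer three stronger things that the documents do not support:
- *The trial is underpowered, or 282 events is the wrong target.* At HR 0.70, 282 events give 85.0%.
- *The 10% sentence is false because 10% means per year.* Annual 10% dropout from randomization would give only about 250–254 events under the same kind of accrual assumption, far from the stated 288, so Table 2 did not use it.
- *The rounding cause is established.* No code is shown; the fit to the printed rates is strong but is still an inference.

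**Conclusion.** Minor, but wrong as written. The Projected and Minimum powers do not follow from the stated constant hazard ratio. The errors are at most about 2 points and run in opposite directions: Projected too favourable, Minimum too unfavourable. Optimistic stands.

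The claim that power exceeds 85% at 10% dropout survives, with a margin of about 0.7 point (85.7%) instead of 2. This rests on the Schoenfeld formula, which reproduces protocol Table 3 and SAP Table 1. Freedman's formula, which does not reproduce Table 3, puts that cell at 85.0% and leaves the direction of every Projected and Minimum gap unchanged.

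The missing dropout unit is a labelling gap. The stated counts do not fit the protocol's 5% per year from randomization. The roughly 277–282 events and 83–85% power for that case depend on an assumed uniform accrual that the documents do not give, so it is a sensitivity case and not a finding that power fell short.

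**What to change.** 1. Rerun the three scenarios at HR 0.70 with unrounded arm rates (about 7.25/10.35, 5.68/8.12 and 7.49/10.71 %/pt-yr).
2. Restate the Projected powers in Table 2 and Appendix I (expected about 87/86/86%) and the Minimum powers in Appendix I (about 80/79/78%), with a note that they correct the March 2021 projection, so that the record of what was computed then is kept.
3. Reword the 10% dropout sentence to give power of about 86%.
4. In Tables 1 and 2 and Appendix I, say whether dropout is cumulative or annual and from what date it applies. Add the protocol's 5% per year from randomization as a sensitivity row, with its accrual assumption stated.

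The cost is one simulation rerun, relabelled columns and one reworded sentence. It needs no added patients or follow-up and no change to the event target.
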